| | Grade 3: serum creatinine (> 3 to $6 \times$ ULN) | 
 Permanently discontinue study drug(s). | 
1-2 mg/kg/day prednisone equivalents^a
 
Consult nephrology
 
Evaluate for other causes (recent IV contrast, medications, fluid status, etc)
 
If improved to Grade 1, taper corticosteroids over at least 4 weeks
 
If elevation persists >3-5 days or worsen, consider additional immunosuppression (e.g. – mycophenolate)
 |
| | Grade 4: serum creatinine ($> 6 \times$ ULN) | 
 Permanently discontinue study drug(s). | 
1-2 mg/kg/day prednisone equivalents^a
 
Consult nephrology
 
Evaluate for other causes (recent IV contrast, medications, fluid status, etc)
 
If improved to Grade 1, taper corticosteroids over at least 4 weeks
 
If elevations persist >2-3 days or worsen, consider additional immunosuppression (e.g. – mycophenolate)
 |
| Rash | Grade 2 | 
 Withhold study drug(s). When symptoms resolve to Grade 0-1, resume vopratelimab. If symptoms do not recur after 1 cycle of vopratelimab, resume ipilimumab/nivolumab.^b | 
Should treat skin with topical emollients, oral antihistamines, and medium- to high-potency topical corticosteroids.
 
0.5 to 1 mg/kg/day prednisone equivalents^a
 |
| | Grade 3 | 
 Withhold study drug(s) until resolution to Grade 0-1. When symptoms resolve to Grade 0-1, resume vopratelimab only; permanently discontinue ipilimumab/nivolumab. | 
Should treat skin with topical emollients, oral antihistamines, and high-potency topical corticosteroids.
 
1-2 mg/kg/day prednisone equivalents^a
 |
| | Grade 4 | 
 Permanently discontinue study drug(s). | 
1-2 mg/kg/day prednisone equivalents^a
 
Admit for inpatient management
 |

| Adverse Event | Toxicity Grade | Dose Modification | Recommended Management ^a |
|---------------|---|---|---|
| Neuropathy | Grade 2 | 
 Withhold study drug(s) until resolution to Grade 0-1; if symptoms persist 2¹ 6 weeks, discuss subject continuation with the Medical Monitor. When symptoms resolve to Grade 0-1, resume vopratelimab. If symptoms do not recur after 1 cycle of vopratelimab, resume ipilimumab/nivolumab therapy.^b Permanently discontinue study drug(s) for related reactions lasting 6 weeks or longer or if the subject is unable to reduce the corticosteroid dose to less than 7.5 mg prednisone or equivalent per day. | 
(peripheral neuropathy) Initial observation OR initiate prednisone 0.5-1 mg/kg (if progressing from mild). Neurontin, pregabalin, or duloxetine for pain
 
(Autonomic neuropathy) Initial observation OR initiate prednisone 0.5-1 mg/kg (if progressing from mild). Neurologic consultation
 |
| | Grade 3 or 4 | 
 Permanently discontinue study drug(s). | 
(Peripheral neuropathy) Neurologic consultation Initiate IV methylprednisolone 2-4 mg/kg Monitor pulmonary function, concurrent autonomic dysfunction, neuropathic pain, constipation/ileus. Offer frequent neurochecks
 
(Autonomic neuropathy) Initiate methylprednisolone 1g IV daily for 3 days followed by oral corticosteroid taper Neurologic consultation
 |
| Encephalitis | New-onset moderate or severe neurologic signs or symptoms | 
 Permanently discontinue study drug(s). | 
If etiologies other than immune-mediated adverse events are ruled out, permanently discontinue study drug(s) and administer 1-2 mg/kg/day prednisone equivalents^a Administer concurrent IV acyclovir until PCR results obtained and negative
 |
| | Immune-mediated encephalitis | 
 Permanently discontinue study drug(s). | 
1-2 mg/kg/day prednisone equivalents^a If limited or no improvement, may offer rituximab or plasmapheresis
 |

| Adverse Event | Toxicity Grade | Dose Modification | Recommended Management ^a |
|-----------------|---------------------------|---|---|
| Uveitis, iritis | Grade 2 | 
 Withhold study drug(s). When symptoms resolve to Grade 0-1, resume study drug(s) only if local immunosuppressive therapy was used. Permanently discontinue ipilimumab/nivolumab if systemic therapy was required. | Urgent ophthalmology referral. Topical corticosteroids, cycloplegic agents, systemic corticosteroids. May resume vopratelimumab once off systemic corticosteroids, which are purely indicated for ocular adverse effects or once corticosteroids for other concurrent systemic irAEs are reduced to :S 10 mg; continued topical/ocular corticosteroids are permitted when resuming vopratelimumab to manage and minimize local toxicity |
| | Grade 3 or 4 | 
 Permanently discontinue study drug(s). | Emergent ophthalmology referral. Systemic corticosteroids (IV prednisone 1-2 mg/kg or methylprednisolone 0.8-1.6 mg/kg) and intravitreal/periocular/topical corticosteroids per ophthalmologist opinion |
| Episcleritis | Grade 2 | 
 Temporarily withhold study drug(s) until after ophthalmology consult. | Urgent ophthalmology referral Topical corticosteroids, cycloplegic agents, systemic corticosteroids |
| | Grade 3 or 4 | 
 Permanently discontinue study drug(s). | Emergent ophthalmology referral. Systemic corticosteroids and topical corticosteroids with cycloplegic agents |
| Other | Grade 2 adverse reactions | 
 Withhold study drug(s) until resolved to Grade 0-1. When symptoms resolve to Grade 0-1, resume vopratelimumab only. If symptoms do not recur after 1 cycle of vopratelimumab, resume ipilimumab/nivolumab. If symptoms persist 2' 6 weeks or unable to reduce the corticosteroid dose to less than 7.5 mg prednisone or equivalent per day, subject continuation must be discussed between the Investigator and Medical Monitor | If symptoms persist > 5 days or recur, consider 0.5-1 mg/kg/day prednisone equivalent followed by corticosteroid taper If symptoms persist 2' 6 weeks obtain organ class consultation |

| Adverse Event | Toxicity Grade | Dose Modification | Recommended Management ^a |
|---------------|---|--|---|

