10.8.3 Grading and Severity

Grade refers to the severity of the AE/SAE. Severity will be assessed in this study using the National Cancer Institute (NCI) Common Terminology Criteria for Adverse Events (CTCAE), version 5.0 (see [Appendix 3](#)).

In the event that an AE is not covered by the CTCAE, the assessment of severity will be determined by using the CTCAE general guideline:

Table 2: Grading for Events Not Covered By the CTCAE

| | |
|---------|--|
| Grade 1 | Mild; asymptomatic or mild symptoms; clinical or diagnostic observations only; intervention not indicated. |
| Grade 2 | Moderate; minimal, local or noninvasive intervention indicated; limiting age-appropriate instrumental ADL*. |
| Grade 3 | Severe or medically significant but not immediately life-threatening; hospitalization or prolongation of hospitalization indicated; disabling; limiting self-care ADL**. |
| Grade 4 | Life-threatening consequences; urgent intervention indicated. |
| Grade 5 | Death related to AE |

Activities of Daily Living (ADL)

*Instrumental ADL refer to preparing meals, shopping for groceries or clothes, using the telephone, managing money, etc.

**Self-care ADL refer to bathing, dressing and undressing, feeding self, using the toilet, taking medications, and not bedridden.

The Investigator will evaluate all AEs as to their severity.

- An AE that is assessed as severe should not be confused with an SAE. Severity is a category used for rating the intensity of an event; both AEs and SAEs can be assessed as severe. An event is described as 'serious' when it meets one of the pre-defined outcomes as described in [Section 10.9](#).

Worsening of a pre-treatment event, after initiation of study drug(s) must be recorded as a new AE.

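### Table 1 ties the permanent stop in the first Encephalitis row to two different triggers, and leaves unclear whether vopratelimab may resume after systemic therapy for Grade 2 uveitis

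*Protocol*

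**What the plan says.** Protocol Section 7.1.4.1 refers to Table 1 for vopratelimab dose modification and toxicity management. Each row has a Dose Modification column and a Recommended Management column.

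**Encephalitis, first row.** The trigger is "New-onset moderate or severe neurologic signs or symptoms". The Dose Modification cell orders permanent discontinuation of study drug(s) and adds nothing else. The Recommended Management cell says: "If etiologies other than immune-mediated adverse events are ruled out, permanently discontinue study drug(s) and administer 1-2 mg/kg/day prednisone equivalents". It also calls for antiviral cover until a PCR result is negative. A second Encephalitis row covers the confirmed immune-mediated diagnosis.

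**Uveitis, iritis, Grade 2.** After a hold, the Dose Modification cell says: "When symptoms resolve to Grade 0-1, resume study drug(s) only if local immunosuppressive therapy was used". Its last sentence permanently stops ipilimumab/nivolumab where systemic therapy was needed, and does not name vopratelimab. The Recommended Management cell lists systemic corticosteroids among the treatments and says: "May resume vopratelimumab once off systemic corticosteroids" (the drug name is spelled that way in the table).

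Protocol Section 6.1 defines study drug(s) as vopratelimab together with any partner drug from the parent study.

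SAP Section 3.1 places discontinuation due to adverse events in the primary endpoint. Protocol Section 11.1 lists the reason for discontinuing the investigational drug among the endpoints.

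**The concern.** For a subject with new neurologic signs and no diagnosis yet, one column has already ended treatment. The other has not, because its condition is still open. The protocol foresees this situation: the Management cell itself contemplates other causes and a pending test. Because confirmed immune-mediated encephalitis has its own row, the first row must serve the undiagnosed presentation, which is where the columns part.

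For Grade 2 uveitis the question is whether vopratelimab may resume at all after systemic corticosteroids. The literal resume condition in one column says no, and the other column says yes.

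The ambiguity matters in both directions. The study exists to give continued access to subjects who are benefiting (Protocol Section 2), and a permanent stop ends that access. A resumption re-exposes a subject after a neurologic or ocular event. On the statistical side, whether an event becomes an adverse-event discontinuation could turn on the column that was read rather than on what happened to the subject.

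**Working it through.** No arithmetic applies: the point rests on no rate, event count or sample size. The check sets the two columns of each row against each other for every situation the row can meet.

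**Step 1. First Encephalitis row**

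| Situation | Dose Modification column | Recommended Management column | Agree? |
|---|---|---|---|
| Work-up not complete | Permanent stop | Condition not yet met; no dosing instruction | No |
| Non-immune causes excluded | Permanent stop | Permanent stop | Yes |
| Non-immune cause found | Permanent stop | Condition not met; no dosing instruction | No |

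The columns agree in one of three situations. In the other two, the Management column neither stops the drug nor says that it is held or continued.

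**Step 2. Uveitis/iritis, Grade 2**

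| Therapy used | Drug | Dose Modification column | Recommended Management column | Agree? |
|---|---|---|---|---|
| Local only | Vopratelimab | Resume at Grade 0-1 | Topical/ocular steroids may continue on resumption | Yes |
| Local only | Partner | Resume at Grade 0-1 | No rule | No conflict |
| Systemic | Partner | Permanent stop | No rule | No conflict |
| Systemic | Vopratelimab | Literal resume condition not met; no permanent stop written | May resume once off systemic corticosteroids | No, on the literal text |

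The problem is confined to one drug in one situation. It depends on the Section 6.1 definition, which brings vopratelimab within study drug(s).

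**Step 3. Does any text rank the columns?** None was found. The word Recommended in the second heading might suggest that this column is advisory on dosing. But the Grade 2 nephritis row places a permanent stop of study drug(s), for worsening or non-improving events, only in its Management column. That column therefore carries dosing rules elsewhere in the same table.

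**Step 4. Does any other section settle it?**
- Sections 7.1.4.2 and 7.1.4.3 send nivolumab and ipilimumab dose modifications to their prescribing information and set the order of restart after a hold. They do not say when vopratelimab is stopped for neurologic signs, or whether it may restart after systemic therapy for uveitis.
- Section 7.1.4 requires changes to dose and schedule to be discussed with the medical monitor. Section 8 asks for discussion before withdrawal where possible. Section 13.7 lets sites ask for clarification. None of these supplies the missing rule.
- Several other Table 1 rows name the medical monitor as the person to consult on continuing. Neither of these two rows does.

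**The case against.** **The uveitis row can be read coherently.** After local therapy only, the full regimen resumes. After systemic therapy, the partner drug stops for good and vopratelimab alone may return once the subject is off systemic corticosteroids. The partner-only stop sentence supports this, since it would add little if the resume condition already barred every drug. This largely stands. It makes the row ambiguous rather than flatly contradictory, but it requires reading the resume condition more loosely than it is written.

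**Safeguards exist and the reporting effect is modest.** Sites can consult the medical monitor, which should reduce divergence. There is no hypothesis test or planned sample size, and adverse events are reported as listings plus one overview table (SAP Section 6.6.1.2). That section also places holds and permanent discontinuations in a single category, so an overview count may not show the difference. This stands as a limit on size. It does not remove the issue: discontinuation is named in the primary endpoint, and SAP Section 6.4.1 summarizes reasons for treatment discontinuation.

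**A reader might infer that the Encephalitis row also contradicts Grade 2 neuropathy.** The trigger is worded as moderate neurologic signs, and Protocol Section 10.8.3, Table 2, describes Grade 2 as "Moderate; minimal, local or noninvasive intervention indicated; limiting age-appropriate instrumental ADL". The Grade 2 neuropathy cell says "When symptoms resolve to Grade 0-1, resume vopratelimab. If symptoms do not recur after 1 cycle of vopratelimab, resume ipilimumab/nivolumab therapy". The documents do not establish a conflict. The row sits under the Encephalitis heading with an encephalitis work-up, and neuropathy has its own graded rows. Table 2 is for events that CTCAE does not cover, whereas Table 1 is graded by CTCAE version 5.0. The neuropathy cell is also not simply a resumption rule: it includes "Permanently discontinue study drug(s) for related reactions lasting 6 weeks or longer", and a stop for subjects who cannot reduce their steroid dose. The overlap is a possible reading only.

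**Conclusion.** The point holds in two parts of unequal strength.

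- **First Encephalitis row: a real conflict in the current text.** The columns give different triggers for the same permanent stop, and the dosing status during work-up is not stated. If the cause proves immune-mediated, both columns end in a permanent stop.
- **Grade 2 uveitis/iritis: a secondary point.** It is limited to whether vopratelimab may resume after systemic therapy. The row is inconsistent on the literal text and ambiguous at best.

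A reader might go further and say that each event means either permanent loss of all study drugs or a hold or resumption. The text does not support that. No Grade 2 uveitis wording permanently stops all study drugs, and no wording in the first Encephalitis row says hold or resume. Nor does the Management column say that a subject stays on treatment during work-up; it is silent.

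Size cannot be given as a number. The documents state no frequency for either event and do not say how often new neurologic signs have a non-immune cause. The effect on the discontinuation component of the primary endpoint rests on the assumption that at least one such event occurs and that sites read the columns differently. The correction is worth making because it is cheap and concerns safety instructions, not because a measurable bias has been shown.

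**What to change.** Amend Table 1 as follows:

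1. In the first Encephalitis row, state the trigger for permanent discontinuation once, identically in both columns. State the dosing status while the work-up is under way and what applies if a non-immune cause is found.
2. In the Grade 2 uveitis/iritis row, give vopratelimab and the partner drug one stated rule each after systemic therapy, and make both columns agree.
3. Optionally, add a line clarifying that the Encephalitis row does not capture events graded under Neuropathy.

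The sponsor's medical lead decides which rule applies in each case; the request here is only that the passages be reconciled. The cost is an edit to a few table cells in a protocol amendment, with the written agreement and ethics submission that Protocol Section 13.5 requires. No new data collection and no change to the SAP's analyses is needed.

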6.1.1 Contraindications

Based on the immune-stimulatory mechanism of action of vopratelimab, it should not be administered to subjects with any of the following:

Active disease requiring systemic immunosuppressive therapy. Exceptions allowed on a patient by patient basis upon discussion with the medical monitor;

Any known primary or acquired diagnosis of immunodeficiency, or treatment with systemic steroids or any other form of immunosuppressive therapy. Exception: inhaled or topical steroids and adrenal replacement doses are permitted in the absence of active autoimmune disease.

Please refer to the respective prescribing information for contraindications to nivolumab and ipilimumab.

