7.1.4.2 Dose Modifications and Toxicity Management for Vopratelimab in Combination with Nivolumab

For dose modifications for nivolumab please follow the prescribing information ([Opdivo® Full Prescribing Information {Bristol-Myers Squibb Company 2021}](#)). In the event of a toxicity that requires that study treatment be withheld until resolution to Grade 0 or 1, the first administration of study drug after resolution of toxicity should be vopratelimab alone. Nivolumab may be added at the next dose, at the discretion of the investigator and the medical monitor, if the toxicity does not recur with vopratelimab monotherapy.

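### The Grade 2 episcleritis hold in Table 1 ends on a consult rather than on the subject's state, and leaves event grade, steroid use and partner drug open at restart

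*Protocol*

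**What the plan says.** The whole dose-modification entry for Grade 2 episcleritis in Table 1 is "Temporarily withhold study drug(s) until after ophthalmology consult". Its management column calls for urgent referral and lists topical corticosteroids, cycloplegic agents and systemic corticosteroids.

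The row directly above, Grade 2 uveitis/iritis, names the same referral and the same three treatments: "Urgent ophthalmology referral. Topical corticosteroids, cycloplegic agents, systemic corticosteroids". Its dose-modification entry goes further: "When symptoms resolve to Grade 0-1, resume study drug(s) only if local immunosuppressive therapy was used", and "Permanently discontinue ipilimumab/nivolumab if systemic therapy was required". Its management column lets vopratelimab resume "once off systemic corticosteroids, which are purely indicated for ocular adverse effects", with a separate provision for steroids given for other immune-related events.

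The catch-all row for other Grade 2 reactions reads "Withhold study drug(s) until resolved to Grade 0-1", followed by vopratelimab alone and then the partner drug if symptoms do not recur after one cycle.

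The general sections also bear on restart:
- Section 6.1.1 says vopratelimab should not be given to subjects with immunodeficiency, "or treatment with systemic steroids or any other form of immunosuppressive therapy". Section 6.1.2.1 prohibits the same medication.
- Section 6.1.2.2 lists oral steroids among permitted medications.
- Table 1 footnote b requires Grade 0-1 and less than 7.5 mg/day prednisone equivalent before treatment resumes. The mark is not on the episcleritis row.
- Section 7.1.4.2 says that, after a hold that runs to Grade 0 or 1, "the first administration of study drug after resolution of toxicity should be vopratelimab alone". Section 7.1.4.3 says the same for ipilimumab.

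**The concern.** A hold that ends at an appointment says nothing about whether the event has improved, what immunosuppression the subject is taking, or which drugs come back. One investigator can follow the episcleritis row and re-dose after the consult. Another can apply Section 6.1.1 or borrow the uveitis conditions, and wait. Each can point to protocol text.

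Two things are at stake. The first is the safety of a subject whose eye event is unresolved. The second is consistency of the safety data: SAP Section 6.6.1.2 lists TEAEs leading to interruption, reduction, hold or permanent discontinuation and counts them in an overview table, and the primary endpoint in SAP Section 3.1 includes discontinuation due to AEs. If the action taken depends on which passage a site reads, those entries partly reflect site interpretation.

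**Working it through.** The plan gives no figure to reproduce here. The check is a count of Table 1, a comparison of passages, and one timing calculation.

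**Step 1. What ends each temporary hold in Table 1.**
- Grade 0-1: diarrhea/colitis Grades 2 and 3; pneumonitis 2; hepatitis 2; hyperglycemia 2 and 3-4 (with glucose or metabolic control); nephritis 2; rash 2 and 3; neuropathy 2; uveitis/iritis 2; Other 2 and 3. That is 2 + 1 + 1 + 2 + 1 + 2 + 1 + 1 + 2 = 13 rows.
- Stabilized on replacement hormone: hypophysitis 2-3 and 4; adrenal insufficiency 2 and 3-4. That is 4 rows.
- Symptoms back to baseline: hypothyroidism and hyperthyroidism. That is 2 rows.
- Consult has taken place: episcleritis 2. That is 1 row.

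Total: 13 + 4 + 2 + 1 = 20 rows. Nineteen depend on the subject's state and one on a procedure. The six endocrine and thyroid rows have no Grade 0-1 rule either, but each adds a discussion with the medical monitor before combination therapy resumes.

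**Step 2. Restart conditions side by side.**

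| | Episcleritis, Grade 2 | Uveitis/iritis, Grade 2 | Other, Grade 2 |
|---|---|---|---|
| End of hold | Consult | Grade 0-1 | Grade 0-1 |
| Steroid condition | None stated | Off systemic steroids given for the eye event | Medical Monitor discussion if not below 7.5 mg/day prednisone equivalent |
| Partner drug | Not stated | Stopped permanently if systemic therapy was needed | Added after one cycle without recurrence |

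**Step 3. Staged restart.** Sections 7.1.4.2 and 7.1.4.3 apply when a toxicity requires a hold to Grade 0 or 1. The episcleritis hold is not of that kind, so on its wording it does not call up the vopratelimab-alone dose.

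**Step 4. Can the steroid conflict arise in ordinary use?** Footnote a is attached to the management column heading and asks for a taper of at least 4 to 6 weeks, or per institution guidelines. Let I be the dosing interval, t the weeks since the last dose when steroids start, and L the taper length. The next scheduled dose falls inside the taper if I − t < L.
- q3w, L = 4: 3 − t is at most 3, which is less than 4, so the dose always falls inside.
- q6w, L = 4: 6 − t < 4 when t > 2 weeks.
- q6w, L = 6: 6 − t < 6 whenever t > 0.

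This assumes that systemic steroids are used, that the taper lasts at least 4 weeks, and that dosing is on schedule. A shorter institutional taper could avoid the overlap. Where the overlap occurs, the row does not stop the vopratelimab dose, Sections 6.1.1 and 6.1.2.1 do, and Section 6.1.2.2 would allow it if the steroid is oral.

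**The case against.** The strongest reply is that the row sets a minimum hold and never says to resume, unlike the uveitis and Other rows. That stands. A reader might infer that the protocol directs the full combination to be restarted at Grade 2 with systemic steroids running. It does not: the row fails to prevent this, and other sections pull against it. Section 7.1.4 also requires any change of dose or schedule to be discussed with the medical monitor, which arguably covers restart after a hold, but it supplies no restart criterion.

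Second, the steroid conflict is not peculiar to episcleritis. Section 6.1.2.2 permits oral steroids, and footnote b allows resumption below 7.5 mg/day on rows that carry it, so the steroid rules disagree across the protocol. Footnote b is also missing from other hold rows, so its absence here is not distinctive in itself. This stands, and it widens the reconciliation that is needed.

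Third, different diagnoses may deliberately have different rules, a specific row overrides a catch-all, and listing systemic steroids under recommended management does not mean every subject gets them. This is fair: the Other row is context rather than a contradiction. But the documents give no reason for the difference between the two eye rows, and an intentional difference would still leave the row silent on steroids that it lists itself.

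Fourth, Sections 7.1.4.2 and 7.1.4.3 send nivolumab and ipilimumab modifications to prescribing information that is not in these documents. What happens to the partner drug therefore cannot be settled here. Monotherapy subjects have no partner drug, and ipilimumab is given in sequence, so a simultaneous restart is not a general description.

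**Conclusion.** The point holds as an inconsistency and a gap. One hold row in 20 ends on a procedure, does not rule out re-dosing with the event still Grade 2, bypasses the staged restart on its wording, and lists a treatment that two sections bar with vopratelimab and a third partly permits. The near-identical uveitis row answers the questions this row leaves open.

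Three further inferences are not supported:
- That the row conflicts with the whole of the rest of the protocol. Six endocrine and thyroid rows also lack a Grade 0-1 condition.
- That holds and interruptions are part of the primary endpoint. SAP Section 3.1 includes only discontinuation due to AEs; holds and interruptions appear in the listings and overview table.
- That subjects would typically miss no dose. This needs an assumed referral time, and a state-based hold that resolves between doses would miss none either.

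The documents give no expected frequency of Grade 2 episcleritis, so the number of subjects affected cannot be stated. No sample size or power figure depends on this. The case for acting rests on patient safety and uniform conduct across sites, at the cost of a small edit.

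**What to change.** Reconcile the Grade 2 episcleritis row with the Grade 2 uveitis/iritis row, footnote b, and Sections 6.1.1, 6.1.2.1, 6.1.2.2, 7.1.4.2 and 7.1.4.3, so that the row and the general sections give one consistent instruction on resumption, steroid use and the partner drug. The sponsor's clinical team decides which rule stands. If the consult-based hold is intended, the protocol should say so and state how it sits with the steroid provisions and the staged restart. The cost is the wording of one table row, with cross-references or conforming edits to the steroid sections, in the next amendment. No analysis in the SAP has to change.
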